8.4. Randomisation procedure

Participants will be randomised online using the REDCap Academic randomisation software. Participants who complete the screening process, provide informed consent, complete the baseline dataset and assessments, including a minimum of 36 EMA prompts, will be eligible to be randomised.

Randomisation will be completed following submission of the required data. Upon randomisation, an automated email notification will be sent to the Chief Investigator, the trial manager/trial management team (at ExeCTU), the PWPs (UK)/coaches (USA) and the participant. The email notification to the PWPs/coaches will contain the randomised allocation (The PWP/coach will be assigned prior to knowledge of the allocation group). All other recipients will receive blinded notifications. The participant's email will contain instructions for the next steps, including how to reinstall mPath with a new invitation code to start the series of follow-up surveys, and to anticipate a set up email from MyDataHelps and contact from the PWP/coach.

There will not be a process for emergency unblinding of a participant's allocation because PWPs/coaches will already know the allocation. In the event that a participant is at risk of self-harm or suicide, their management will not be dictated by knowledge of their allocated group. Participants will be managed according to a standard operating procedure for managing people at risk, irrespective of intervention allocated or received.

Randomisation will be managed by discrete REDCap instances in the UK and the USA. Each country will have separate randomisation lists provided by the senior trial statistician based at ExeCTU (see Section 5.1.1 Randomisation). Stratification factors will be pulled directly from the baseline data entered into REDCap by the participant. Stratification will be location (UK versus USA) and caseness or not for depression (PHQ-9 \leq 9 versus >9) or anxiety (GAD-7 \leq 9 versus >9).

The randomisation allocation will be automatically communicated to the MyDataHelps platform via an API, including the participant ID number and email address. This will ensure the participant only has access to the specific variants of the modules as per their allocation. The email address is necessary for the participant to set up their account on MyDataHelps. During account set-up, the participant will also be able to volunteer their name and phone number if they wish to receive personalised messages (i.e., reminder prompts) directly from MyDataHelps.

Randomisation to particular intervention condition will be independent of allocation to study PWP/coach. Allocation to PWP/coach will be conducted independently and with concealment of randomisation (i.e. PWPs/coaches will be allocated to next sets of patients before randomisation is known). All PWPs/coaches will provide all variants of the online therapy, with the assumption that across the study this will be balanced given the randomisation to intervention condition and large numbers of participants per PWP/coach.

8.5. Follow up data collection

8.5.1. Weekly micro-assessments (during the intervention stage)

At week 1, 2, 3, 4, 5, 7, 9, 11, 13, 15, participants will receive prompts to complete brief questionnaires (micro-assessments) via the mPath App. The schedule for these questionnaires will start from the day the participant reinstalls mPath with their second invitation code, provided to them at the point of randomisation. The questionnaires collected during the micro-assessments will include condensed (2-3 item versions) of self-report and brief problem description measures of mediators, as well as brief outcome measures of RNT, anxiety (GAD2), depression (PHQ2), as detailed in Table 3. Participants will also be prompted to complete two brief questions in weeks that the full micro-assessment is not required (weeks 6, 8, 10, 12 and 14). This is to maintain engagement and to keep m-Path live on their phones (i.e., prevent the App from being put to sleep by the operating system).

Participants will have a +4 day window each week to complete the micro-assessments, after which the assessment will no longer be accessible to the participant. If any of the micro-assessments or engagement prompts are not completed, the participant will be sent an email to increase their engagement with the app and reminding them to open the m-Path app to ensure future survey notifications are received (i.e. to avoid the app going into sleep mode).

During the intervention period we will also collect data on engagement with the intervention (see Section 9 for more details).

8.5.2. 16 weeks post-randomisation

At 16-weeks post randomisation, participants will receive an automated SMS text message and an email with a link to complete the follow up questionnaires as surveys via REDCap Academic. On week 16 participants will also be invited to complete EMA for another 10-14 days (see the EMA thresholds under the Baseline Section 8.3) via the m-Path App. The schedule for the EMA will start from the day the participant reinstalls mPath with their second invitation code, provided to them at the point of randomisation. The questionnaires and data collected at 16 weeks post-randomisation are detailed in Table 3.

Participants will have a +4 week window to complete the questionnaires. During the 4-week window, participants will receive up to 3 SMS text messages and 3 email reminders to prompt them to complete the questionnaires. Participants who have not completed the questionnaires after receiving the reminders may be telephoned up to three times by the research team (postgraduate researchers) to encourage and support the participant to complete the questionnaires. The researchers will support participants in completing the assessments during the call, understand any barriers to completion, directly send them the link to complete the assessment if needed, and as a final step only collect the primary outcome data directly over the phone.

If a participant completes one of the questionnaires with data that indicates they could be at risk of self-harm and/or suicide, additional questions about their immediate risk will be triggered. A separate study risk protocol will be followed under these circumstances.

8.5.3. 6 months post-randomisation

No data will be collected 6 months post randomisation but as there is a large gap between the 16-week and 52-week data collection timepoints participants will be sent a 6-month email as a simple

touch point to keep the participant engaged. This will act as a reminder that we will be in contact with them to complete their final questionnaires at 52-weeks after randomisation.

8.5.4. 52 weeks post randomisation

At 52-weeks post randomisation, participants will receive an automated SMS text message and an email with a link to complete the follow up questionnaires as surveys via REDCap Academic. The questionnaires and data collected at 52 weeks are detailed in Table 3.

Participants will have a +6week window to complete the questionnaires. During the 6 week window, participants will receive up to 3 SMS text messages and 3 email reminders to prompt them to complete the questionnaires. Participants who have not completed the questionnaires after receiving the reminders may be telephoned up to three times by the research team (postgraduate researchers) to encourage the participant to complete the questionnaires, support in completing the assessments during the call, understand any barriers to completion, directly send them the link to complete the assessment if needed, and as a final step only collect the primary outcome data directly over the phone.

If a participant completes one of the questionnaires with data that indicates they could be at risk of self-harm and/or suicide, additional questions about their immediate risk will be triggered. A separate study risk protocol will be followed under these circumstances.

8.6. End of study

The study will end for a participant once their 52-week follow-up questionnaires and data collection are complete, or sooner if the participant opts to withdraw their consent to participate before the end of the study.

The study will end overall once all follow-up are complete (or if not completed, when the final follow-up window has expired), the data has been checked and cleaned and both instances of the REDCap Academic EDC have been locked in the UK and the USA, respectively.

9. STUDY TREATMENT DELIVERY

The intervention is primarily an online digital platform (MyDataHelps) delivering modules of CBT that participants complete in a self-directed manner. The intervention is accessed through a web browser/app. See section 8.4 for details of how the allocation is communicated to the platform and how the participant accesses it.

The intervention is supported by a minimum of three sessions with a PWP (UK)/coach (USA) (see Section 4.1 for details) delivered by video or telephone call.

Adherence to the digital intervention will be measured by collecting data on; a. number of PWP/coach contacts attended, b. number of online CBT sessions completed, and c. number and frequency of tools (self-practice element in app) completed as a minimum, with more detailed analyses examining completion of specific sections within the online sessions. The target would be for participants to complete at least 50% of the online sessions (i.e., 3 of 6). A contact log will document interactions between PWPs/coaches and participants and the reasons for any missed contact sessions.

USA-specific detail

Coaches in the USA will be responsible for setting up their local participants on MyDataHelps and conducting the contact sessions.

10. PROCESS EVALUATION

To inform understanding of mechanisms and barriers and facilitators of sustained implementation within a mixed model approach, semi-structured online or telephone interviews will be conducted with 30 UK study participants around the 16 weeks and 12 months timepoints. These will be conducted after the participant has completed their follow-up questionnaires (or the time window for completion has elapsed) for the relevant follow-up timepoint. The same participants will be interviewed at both timepoints where possible; when attrition occurs, we will make up the sample with further participants. The sampling strategy will include participants who have received at least three of the different intervention components to enhance our ability to investigate interactions between elements. Within this criteria, we will also sample for those who make the most/least progress on the core outcome measures (measured through EMA/PTQ), as well as sampling for maximum variation in t, socio-economic group, age, and ethnic heritage. Interviews will examine engagement with the digital platform, acceptability, experiences of any PWP support, how different mechanisms of impact operate to produce outcomes, and any contextual factors.

Qualitative data will be analysed using realist-informed thematic analysis, with NVivo v14, to deductively investigate each of these areas but we will also include an inductive approach to identify any novel findings. Participants who drop out of the intervention will be invited to complete a brief online form with an open question about their reasons for withdrawing; these data will be analysed using framework analysis. We will analyse metrics of digital intervention use (reach, dose, frequency and attrition). Mixed methods analysis will then use matrix and joint-display tables to integrate qualitative and quantitative data (including from psychological measures collected for the study) at case level for each participant and at the intervention level.

11. PARTICIPANT WITHDRAWAL

Participants are able to withdraw from some of all aspects of the study at any time. We will ask for the reason(s) for their withdrawal but participants do not have to provide a reason. The study will adopt the principles of the PerSEVERE guidance⁶⁸ to enable participants flexibility with their participation where it is practical and reasonable to do so. In accordance with regulatory guidance, data that have already been collected will continue to be retained and used in the analysis (this does not include any data collected as part of the qualitative interviews which participants can request deletion of up to the point that the analysis of the data has begun, approximately 2 weeks after each interview).

Participants who withdraw after consent but before randomisation will not count toward the sample size and we will continue to recruit until the target sample size is met with randomised participants.

Participants who withdraw after randomisation will count toward the target sample size and will not be replaced.

Randomised participants can change their participation in the study in the following flexible ways:

- Opt out of the intervention
- Opt out of the follow-up data collection
- Opt out of any qualitative interviews they consented to but have not yet taken part in

- Stop contact from the research team (only if withdrawn from all other components of the study)

Participants who have either completed or opted out of the intervention AND have opted out of follow-up data collection will not be monitored by the research team for risk. The research team will be acting strictly in a research capacity in the study and will not be considered a 'healthcare provider' responsible for providing support or services that would normally be provided by the NHS or other health and social care services. Only participants in active follow-up will be monitored for risk.

When a participant opts to withdraw from one or more component of the study a member of the research team will attempt to contact them to gather more information about which elements of the trial they wish to opt out of. The participant will then be asked to provide freetext reason for their withdrawal via a survey via REDCap Academic, this will be optional. If a participant notifies the research team via any method that they wish to opt out of the study, but declines to complete a Change in Participation form, a member of the research team will complete a form on behalf of the participant and document the communication with the participant in which the request was received. The form will capture whether it was the participant or a member of the research team who completed it.

Randomised participants who opt out of the intervention will have the option to opt back in under their original consent, but only if still within their original intervention time window. Once the participant has reached the 16-week post-randomisation follow-up timepoint, they will not be able to opt back into the intervention. Once the intervention time window has passed, participants will, by default, no longer be able to opt out of the intervention.

Randomised participants who opt out of follow-up data collection will have the option to opt back in under their original consent, providing they have not exceeded the window for the final follow-up at 52-weeks post-randomisation. Participants who opted out after the 16-week follow-up window has expired, and then opt back into the study, will not be able to retrospectively complete the 16-week follow-up data.

Participants will be able to change the communication preferences for study updates and summary study results at any time by contacting the research team. Even if a participant withdraws from active participation in the study, their previously specified communication preferences will be retained unless they actively change them.

The research teams will only withdraw participants under limited circumstances, as detailed below:

- The participant is strongly suspected to be an imposter participant (i.e., a person/bot who has disingenuously enrolled in the study, potentially for financial benefit). Clear documentation will be recorded to capture reasons for believing the participant is an imposter.
- The participant displays threatening or abusive behaviour toward a researcher/PWP/coach. In this situation, the participant would be withdrawn from the intervention and interview (if consented to it) but may still complete follow-up if willing.
- The participant is found to be ineligible (post-consent) in such a way that the intervention is not suitable for them and it would be in their best interest to withdraw.
- The participant loses capacity to consent during their participation in the study.

The CI or site lead will be required to assess and approve any withdrawals of participants proposed by the local research team/PWP/coach. All withdrawals and reasons for them will be reported to and monitored by the TMG, DMEC and TSC.

Randomised participants who are lost to follow-up (i.e. have not completed any or parts of the intervention and/or have not completed follow-up data and who the research team have not been able to make contact with) will not be categorised as withdrawn.

12. SAFETY MONITORING

There is no known health risk associated with any of the assessments or the CBT modules included in the intervention. As such, the risk associated with participation in this study is deemed to be low. Further, we anticipate that the interventions will on average reduce symptoms and improve well-being. CBT is a widely used intervention in NHS and non-NHS settings.

The initial screening process will exclude anyone self-reporting a history of severe psychiatric disorder, alcohol/substance abuse and those reporting elevated suicidality. These individuals will be automatically guided towards appropriate information and sources of help. This process means that individuals likely to have significantly increased risk (e.g., for self-harm and suicidality), and/or for whom more intensive psychological and psychiatric treatment is appropriate, will not be included in the study.

Other than the intervention failing to produce an effect, there is nothing in the literature to suggest possible adverse effects of the assessments and interventions for the participants involved. Versions of components within the intervention have been previously used with no detected harmful effect.

As with all psychological interventions, individuals reflect on their difficulties, which can produce temporary increases in distress, but no more than would commonly occur in daily life. The likeliest outcome for users who do not find the intervention of benefit, or who do not get on well with the assessments, is their disengagement from it. In addition, all participants receive more intensive monitoring, with processes to identify and direct all relevant participants to potential sources of help.

As part of our policy for addressing risk and prioritising the welfare of participants, participants are provided with links to online support, the opportunity to request contact from the study team, and automatic signposting to help and guidance if reporting risk (e.g., suicidal thoughts, as indexed in items within the Patient Health Questionnaire-9 (PHQ-9) on the screening or follow-up questionnaires) or significant worsening symptoms suggesting a need for help. These messages include general information on the presenting symptom, recommended actions to make themselves safe, and advice to seek medical help, and direct links to relevant national sources of help. These sources of support will be tailored by participating country. For this purpose, significant worsening symptoms is defined as a deterioration of movement across two or more score categories on the GAD7 or PHQ-9 from baseline to 16-weeks or from baseline to 52-weeks follow-up. At the point of automated signposting, participants can request contact from a study PWP or contact a study PWP via e-mail or telephone to seek advice.

The main indicator of harm will be the completion of the PHQ-9 questionnaire by the participants at baseline and at 16-weeks and 52-weeks post-randomisation. Questionnaires will be automatically screened for signs of severe distress (for example, defined reports of suicidal ideation), with automatic programmed questions following up to ascertain aspects of risk and to automatically provide users

with recommended advice and signpost towards help (GP, local hospital, crisis teams, relevant charities; e.g., website link to the Samaritans). Other indicators would be reports of worsening symptoms or suicidality in direct contact from participants to the research team or in contact with the study PWP (UK)/coach (USA). For participants at 16-weeks, elevated reports of suicidality (as per definition at screening, i.e., endorsing automated follow-up questions 2 or 3) will be followed up by the associated PWP, following an established risk protocol.

PWPs/coaches will maintain a risk log separate from the research database to document interactions with participants who are (or potentially are) 'at risk' and any actions taken to support, guide and/or refer them on to other services. The risk log will not be considered 'research data', but instead will be data pertaining to the clinical care of the participant

In addition, the number of participants who report significant worsening symptoms of anxiety, or worsening symptoms of depression (as defined above) will be reported to the DMEC, TSC and TMG via regular reports. For all participants, we will include brief open questions at 16-week follow up to assess potential harm from the intervention (e.g., "Have you had any problems with the study treatment? Has any aspect made you feel worse?"), whilst minimizing participant burden. If harm is indicated in these questions, the PWPs will be automatically notified to review the freetext answers and discuss any concerns with the site lead within 3 working days. Number of participants indicating harm in these questions will be reported to the oversight committees via routine reports.

Individuals reporting severe levels of symptoms or meeting diagnostic criteria for depression will be offered guidance to seek appropriate help from their GP or relevant clinical service, should this seem necessary.

For those who are randomised into the study and then indicate risk there will be the option to request contact from a PWP to seek advice. This advice will include guidance for the participant to seek appropriate help from their GP or other relevant services, should this seem necessary. PWPs will be trained in and provided with a protocol to assess risk including standard useful responses in these circumstances. The University of Exeter (UK) study site has a designated site lead/senior clinical psychologist and psychological wellbeing practitioners who will be available as a resource to researchers to provide guidance on clinical issues arising from participants either through standardised measures or contacts initiated by the participant. An equivalent series of expertise is available at UCLA (USA).

If a PWP/coach has serious concerns about a participant, where appropriate, after discussion with a supervisor (e.g. site lead; clinically qualified supervisor), the clinician or PWP/coach will contact the participant (by email or telephone) to review the situation, provide guidance and offer to write a referral letter, subject to participant consent. These procedures will be made explicit in all information sheets and will be detailed in a separate risk protocol. Any concerns detected this way will be recorded on a risk log. The same process will be activated in response to any concerns raised by participants at other times, either spontaneously or in responses during the assessments.

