If a participant discloses suicidality during an encounter with study staff, study staff will provide the participant with information about community and emergency resources, and report to the Coaching Supervisor. Additionally, study staff may provide participant contact information to the IVC Behavioral Intervention Team (BIT) for their team to conduct independent follow up with students.

If during the course of the study a participant's responses to surveys indicate a significant worsening of symptoms, they will be provided with contact information for the IVC health center, as well as community and emergency resources. This is defined as a deterioration of movement across two or more score categories on the GAD7 or PHQ-9 from baseline to 16-weeks or from baseline to 52-weeks follow-up.

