INTERVENTION/TREATMENT PERIOD																				
Allocation				X																
Intervention (via MyDataHelps)					→															
During intervention micro-assessments:																				
PHQ-2				X	X	X	X	X		X		X		X		X		X		
GAD-2				X	X	X	X	X		X		X		X		X		X		

The Calming Minds Trial

IRAS ID: 356635

ISRCTN No: 10569526

	Pre-baseline	Baseline	Allocation	Post-allocation																Follow-up 1	Follow-up 2
				Intervention period																	
TIMEPOINT (t) unit = Days	Undefined	t-28 ^g	t0	t+ 7 ^a	t+ 14 ^a	t+ 21 ^a	t+ 28 ^a	t+ 35 ^a	t+ 42 ^a	t+ 49 ^a	t+ 56 ^a	t+ 63 ^a	t+ 70 ^a	t+ 77 ^a	t+ 84 ^a	t+ 91 ^a	t+ 98 ^a	t+ 105 ^a	t+112 days ^b	t+365 days ^c	
Condensed (2-3 item version) of self report and brief problem description measures of mechanisms and brief outcome measures of RNT				X	X	X	X	X		X		X		X		X		X			
mPath engagement prompts									X		X		X		X		X				
OTHER ACTIVITIES																					
Researcher / PWP (UK) / Coach (USA) contact points		X ^d		X ^e		X ^e						X ^e									
Withdrawals, including free text reasons																					
Participant contact log																					
Qualitative interview																			X ^h	X ^h	
Adverse events																					
Suicide Risk assessment																					

a = Schedule begins when participant reinstalls mPath with code provided at point of randomisation, +4 day window for completion, b = Schedule begins from randomisation for all assessments other than EMA which begins when participant reinstalls mPath with code provided at point of randomisation, +4 week window for completion, c = Schedule begins from randomisation, +6 week window for completion, d = Researcher contact to help participant set up and use mPath App, e = Minimum of 3 sessions planned for approximately at the start of the intervention, 1/3 through and 2/3 through the intervention. Additional sessions may also be scheduled based on participant need. Ad-hoc interactions between PWP/coaches and participants will also occur in response to identification of potential risk/safety events, f = Participant will complete PHQ-9 and if scoring 1 or more on question 9, additional suicide risk questions will be presented, g = Maximum 28 days to complete baseline questionnaires (this period may be extended in extenuating circumstances if requested by a participant). Minimum time to complete baseline is 10 days to allow sufficient time to complete the EMA, h = subset of UK participants only.

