The NIHR BioResource [<https://bioresource.nihr.ac.uk/centres-programmes/mental-health-bioresource/>] is a recallable resource of over 250,000 volunteers, with and without health conditions who have agreed to take part in health-related research. We will apply to use this resource to recruit (final decision on use of this resource will be subject to costs and their agreement to support the study). Within the NIHR Bioresource we would be sending invitations to participants aged 18 years and over who are part of the Genetics Links to Anxiety and Depression (GLAD) study resource and participants of the wider BioResource who are identified as having anxiety and/or depression. Participants in the GLAD trial have been referred through clinics and through self-referral with all participants having mild to moderate anxiety and depression. NIHR BioResource will create a list of potential participants based on our inclusion/exclusion criteria, which is then input into a database. Staff at NIHR BioResource have ethical approval to send out invites (either by email or post), which summarise the study, what's involved, next steps, how to register (including the URL/QR code to the screening survey), contact details for the research team, and they also include a BioResource-specific participant information sheet. If a potential participant is interested in the study, they will use the provided URL to access the self-complete screening survey (REDCap Academic). The research team at University of Exeter will not receive personal identifiable information from participants of the BioResource prior to them completing the screening survey (where they will input an email address).

NHS DigiTrials (England only)

We will potentially use NHS DigiTrials [<https://digital.nhs.uk/services/nhs-digitial>] to send information about the study to potentially suitable/interested people (subject to costs and their agreement to support the study). Through NHS DigiTrials we will obtain support under Regulation 5 of the Health

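### The worsening count sent to the oversight committees cannot register anyone whose baseline is in the top two categories of a scale; under the usual GAD-7 bands that is every anxiety case

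*Protocol*

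**What the plan says.** Section 12 (Safety monitoring) defines significant worsening as "a deterioration of movement across two or more score categories on the GAD7 or PHQ-9", measured from baseline to 16 weeks or from baseline to 52 weeks. Section 2 gives the same rule for the UK and repeats it in its USA-specific detail: "This is defined as a deterioration of movement across two or more score categories on the GAD7 or PHQ-9". The rule triggers automated signposting. Section 12 then reuses it for oversight: "the number of participants who report significant worsening symptoms of anxiety, or worsening symptoms of depression (as defined above) will be reported to the DMEC", and to the TSC and TMG, in regular reports. The protocol gives no cut-points for the categories, and no other worsening criterion for people who already score high.

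High scorers are enrolled. Sections 7.1 and 7.2 set no upper limit on the PHQ-9 or GAD-7 total. Sections 5.1.1 and 8.4 stratify by caseness, defined as a score above 9 on either scale: "Stratification will be location (UK versus USA) and caseness or not for depression" or anxiety. Section 8.1 describes one possible recruitment source as "all participants having mild to moderate anxiety and depression".

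Other safety channels exist:

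- **Suicidality.** The Table 3 notes say "Participant will complete PHQ-9 and if scoring 1 or more on question 9, additional suicide risk questions will be presented". Sections 8.5.2 and 8.5.4 add that, when follow-up answers suggest risk, "additional questions about their immediate risk will be triggered".
- **Severe symptoms.** Section 12: "Individuals reporting severe levels of symptoms or meeting diagnostic criteria for depression will be offered guidance".
- **Harm questions.** Section 12 puts open questions about harm to all participants at 16 weeks and reports the number indicating harm to the committees.
- **SAEs.** Section 12.3 reports them up to 20 weeks after randomisation.
- **Withdrawals.** Section 11 sends these, with reasons, to the TMG, DMEC and TSC.

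**The concern.** A rule based on a rise of two categories has a built-in ceiling. Someone who starts in the highest category, or the one below it, cannot meet it on that scale however much worse they become. Someone in the top two categories on both scales cannot be counted at all. The most symptomatic participants therefore contribute zeros by definition, and nothing in the protocol tells the committees for how many participants the event was impossible.

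This matters because the protocol describes no other routine count of symptom deterioration. Section 12.1 does not record non-serious adverse events, and its list of SAEs contains no symptom-worsening item. A low count could then be read as reassurance about a group in which the count was not able to rise.

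**Working it through.** The protocol states no figure to reproduce here. The check asks, for each possible baseline score, whether any follow-up score would be counted.

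**Inputs**

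- Rule: follow-up category minus baseline category is at least 2 (sections 2 and 12).
- Caseness: above 9 on either scale (sections 5.1.1 and 8.4).
- Assumed bands, because the protocol prints none: GAD-7 0–4, 5–9, 10–14, 15–21; PHQ-9 0–4, 5–9, 10–14, 15–19, 20–27.
- Maximum scores: GAD-7 21; PHQ-9 27, or 24 if item 9 is scored zero.

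**Step 1: any set of bands.** With K ordered categories, a rise of 2 or more is possible only from categories 1 to K − 2. Categories K − 1 and K give no events. This does not depend on the cut-points.

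**Step 2: smallest rise that is counted, under the assumed bands**

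| Baseline | GAD-7 | PHQ-9 |
|---|---|---|
| 0, 1, 2, 3, 4 | 10, 9, 8, 7, 6 | 10, 9, 8, 7, 6 |
| 5, 6, 7, 8, 9 | 10, 9, 8, 7, 6 | 10, 9, 8, 7, 6 |
| 10, 11, 12, 13, 14 | none | 10, 9, 8, 7, 6 |
| 15 and above | none | none |

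- GAD-7: baselines 10–21 are uncountable. These are 12 of the 22 possible scores and all 12 scores in the caseness range.
- PHQ-9: baselines 15–27 are uncountable. These are 13 of the 28 possible scores and 13 of the 18 in the caseness range. Baselines 10–14 remain countable.

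**Step 3: largest rise that goes uncounted from an uncountable baseline**

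- GAD-7: 21 − 10 = 11 points.
- PHQ-9: 24 − 15 = 9 points with item 9 at zero; 27 − 15 = 12 points otherwise.

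By contrast, GAD-7 9 to 15 and PHQ-9 14 to 20 are each counted with a rise of 6 points.

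**Step 4: where the rule, and not the end of the scale, causes the loss.** Six points is the smallest rise that the rule ever counts. Among uncountable baselines, there is still room for a rise of 6 or more at:

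- GAD-7: up to 21 − 6 = 15, so baselines 10–15.
- PHQ-9, item 9 at zero: up to 24 − 6 = 18, so baselines 15–18.
- PHQ-9, item 9 free: up to 27 − 6 = 21, so baselines 15–21.

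Above those scores no rule of 6 or more points could fire either.

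**Step 5: a side effect of the band edges.** Even from a countable baseline a rise of 9 points can be missed (0 to 9, or 5 to 14). A point-increase count would remove this too.

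**The case against.** The strongest reply is that this is one supplementary count within a wider safety system. Section 12 names the PHQ-9 itself as the main indicator of harm, and the two-category rule was written for signposting. Severe symptoms bring guidance whatever the change. The week-16 harm questions are not limited to depression, and their count goes to the committees. Concerns raised with staff or in assessments start the risk process. The DMEC can request analyses (section 13.4) and sees unblinded disaggregated data (section 15). Report tables are often set out in a DMEC charter or monitoring plan, which are not shown.

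Much of this stands, and it limits the consequence. It does not repair the count. Item 9 concerns suicidality and does not pick up worsening of anxiety alone. The harm questions are asked only at 16 weeks and rely on the participant attributing harm to the treatment. SAE reporting ends at 20 weeks. Severe-symptom guidance gives the committees no measure of change. A committee is also less likely to ask for more when the number in front of it looks low.

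Three narrower points:

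- **A looser reading.** If the rule meant moving from one category into the next, only the top category would be blind: GAD-7 15–21 (7 of 12 case-range scores) and PHQ-9 20–27 (8 of 18). That strains the wording and still leaves a gap.
- **The recruitment source.** It is conditional on costs and agreement, and under the assumed bands mild to moderate PHQ-9 scores (5–14) are countable, so it supports the point for GAD-7 only. The enrolment argument rests on the eligibility criteria and the strata.
- **Either scale qualifies.** An anxiety case can still be counted through PHQ-9 if the PHQ-9 baseline is below 15. Section 12 names anxiety and depression worsening separately, however, and an anxiety count could contain no baseline anxiety case.

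**Conclusion.** The concern holds. On the plain reading of the rule, a baseline in the top two categories of a scale gives a structural zero on that scale, and this is true for any cut-points. That the uncountable range is the whole of GAD-7 caseness, and PHQ-9 15 or more, rests on the usual bands, which are assumed.

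The consequence is limited. The protocol gives no baseline distribution, so no number of missed worsenings can be stated. Caseness is a stratification factor, so no bias between factor levels is claimed, and the final inference is not affected. The loss is sensitivity in one routine safety count, for participants in whom the committees would particularly want to see deterioration. It should be corrected because the correction is cheap.

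**What to change.** Keep the two-category count and add to the routine reports:

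1. The number of participants with a pre-set point increase on each scale, applied at every baseline level. The clinical leads and the DMEC should agree the threshold before the first report; none is proposed here.
2. Raw PHQ-9 and GAD-7 change from baseline, by caseness stratum.
3. Beside the two-category count, the number of participants for whom a two-category rise was possible on each scale.

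State the score categories in the protocol. Show any split by factor level only in the DMEC's unblinded report.

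Moving to a one-category rule would not be enough, because the top category would remain uncountable.

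The cost is some extra reporting from data already collected at baseline, 16 and 52 weeks, agreement on one threshold per scale, and a small text amendment through the UK and UCLA routes in section 17.10. Participants do nothing new and the final analysis does not change.
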